**b- How will **eligibility** be determined, and by whom?**

Eligibility to participate will be determined by the PI of this study after completion of the medical and psychiatric evaluation of the potential participant. The PI has both neurology and internal medicine training.

**c- **Risks:** Describe the reasonably foreseeable risks, including risks to subject privacy, discomforts, or inconveniences associated with subjects participating in the research.**

**Risks associated with screening and evaluation.**

During the screening interview, we will ask about psychiatric and medical history. Certain questions may make subjects uncomfortable or anxious. Only trained and experienced research assistants will perform these interviews, which will be done in a sensitive and gentle manner.

**Risks associated with worsening of Alzheimer’s Symptoms:**

Signs and symptoms of Alzheimer’s dementia might be exacerbated as a consequence of study participation either due to the fatigue, pain, or disruption of normal routine related to study procedures or due to the direct effects of endotoxin administration.

The presence of acute or chronic deterioration will belong to one of the following scenarios:

- 1- There are changes in cognition but no changes in ADLs: the patient will be seen in the clinic by [name] within two weeks, a cognitive neurologist, and appropriate medical interventions and follow-up arrangements will be made.
- 2- There are changes in cognition, there are changes in ADLs, but there is no change to the level of care or the ability of the carer to continue to care for the subject: the patient will be seen emergently in the clinic (within 48 hours) and appropriate arrangements will be made. Follow-up will track resolution.
- 3- There are changes in the level of care or the ability of the carer to care for the subject: we will admit the patient into the hospital and provide appropriate treatments and case management.

**Risks associated with confidentiality.**

Although all information collected about each subject in this study will be protected by HIPAA and stored in locked cabinets and in password-protected computers, it is possible that information could be accessed by individuals who are not part of the study team. Such illegitimate access could have deleterious consequences for the subjects with regards to employment, access to health insurance, and stigma. The protection of subject information is not absolute.

It does not apply to any State requirement to report certain communicable diseases or to report cases of physical or sexual abuse. Such duty to report will be explained to each subject during the consent process and if reporting becomes necessary, we will inform the subject. We may release information that identifies subjects in some circumstances, without their permission. For example, we may disclose medical information in the event of an emergency. We may take steps, including notifying the authorities, to protect the subject or someone else from serious harm (including child abuse and elder abuse).

**Risks associated with blood drawing and with IV and radial catheter placement.**

Blood drawing and venous catheter insertion can be associated with mild pain, bruising, infection, or clot formation. These risks are minimized by the use of proper technique. No more than a total of 150 mL of blood will be drawn during the entire study. This amount of blood loss over a period of 10 or more days should have no deleterious consequences in a non-anemic individual. On the morning of the PET scan, a radial artery catheter will be inserted by an experienced healthcare provider. The site will be anesthetized with lidocaine prior to arterial line insertion.

The arterial line will remain in place for the duration of the [11C]PBR28 scans, after which it will be removed. Arterial sampling may be associated with mild-to-moderate pain or bruising at the puncture site. In rare instances, blocking of the artery, poor healing, hematoma, inflammation, or infection at the catheter insertion site may occur. Certain individuals may feel light-headed during arterial catheter placement.

Risks of radial artery cannulation are minimized by having the procedure performed by an experienced health care provider. The health care provider would be either a physician or an advanced practice registered nurse (APRN) with experience in critical care and placement of arterial catheters, as is the practice at Yale-New Haven Hospital. For an APRN to place the arterial line at the Yale PET Center, they must meet the following criteria:

- 1.) Be currently credentialed at Yale-New Haven Hospital or similar institute and
  - 2.) Perform 3 arterial line procedures supervised by a currently privileged PET Center physician
- The 3 supervised arterial line placements will be documented and signed off by both the APRN and supervising physician. The completed document must be on file at the Yale PET Center prior to an APRN performing any arterial line catheterizations independently.

**Risks associated with optional CSF Collection**

-Post-lumbar puncture headache. Up to 25 percent of people who have undergone a lumbar puncture develop a headache afterward due to a leak of fluid into nearby tissues. The headache typically starts several hours up to two days after the procedure and may be accompanied by nausea, vomiting and dizziness. The headaches are usually present when sitting or standing and resolve after lying down. Post-lumbar puncture headaches can last from a few hours to a week or more. See below for mitigation.

-Back discomfort or pain. The patient may feel pain or tenderness in his/her lower back after the procedure. The pain might radiate down the back of his/her legs.

-Bleeding. Bleeding may occur near the puncture site or, rarely, into the epidural space.

-Brainstem herniation. Increased pressure within the skull (intracranial), due to a brain tumor or other space-occupying lesion, can lead to compression of the brainstem after a sample of cerebrospinal fluid is removed.

**Risks associated with radiation.**

The Yale University Radioactive Drug Research Committee (RDRC) will review the use of radiation in this research study, and no subjects will be enrolled until RSC approval is obtained. This research study involves exposure to radiation from two 20 mCi doses of [11C]PBR28 and from the transmission PET scanning. This radiation exposure is not necessary for medical care and is for research purposes only. The amount of radiation subjects will receive in this study is below the dose guidelines established by the federal government and adhered to by the Yale University Radioactive Drug Research Committee (YU RDRC) for research subjects. This guideline is an effective dose of 5 roentgen equivalents in man (rem) per scan and 15 rem/year. The targeted amount of radiation an individual subject will receive in this study is from two injections of 20 mCi of [11C]PBR28, for a total of 40mCi of [11C]PBR28. Although each organ will receive a different dose, the targeted amount of radiation exposure subjects will receive

from this study is equal to an effective dose equivalent of 1.628 rem. This calculated value is used to relate the dose received by each organ to a single value.

In addition to the values given above, subjects who have an C-PIB-PET scan under this protocol may be exposed to radiation from one 15mCi injection of C-PIB. This radiation exposure is not necessary for medical care and is for research purposes only. Subjects who undergo the C-PIB scan will receive a total of 15mCi C-PIB and 40mCi C-PBR. Although each organ will receive a different dose, the targeted amount of radiation exposure subjects will receive from this study is equal to an effective dose equivalent of 1.888 rem. The amount of radiation subjects will receive in this study is below the dose guidelines established by the federal government and adhered to by the Yale University Radioactive Drug Research Committee (YU RDRC) for research subjects. This guideline is an effective dose of 5 roentgen equivalents in man (rem) per scan and 15 rem/year

In situations where a PET scan is not successful following the radiotracer infusion (e.g., problems with the PET camera) the subject may receive an additional radiotracer infusion(s), if deemed appropriate. If an additional injection is completed and the C-PIB-PET scan **WAS NOT** performed, subjects would receive a total radiation dose of 2.44 rem. If an additional injection is completed and the C-PIB-PET scan **WAS** performed, subjects would receive a total radiation dose of 2.70 rem.

The effects of radiation exposure on humans have been studied for over 60 years and no harmful effect to humans has been observed from the levels of radiation subjects will receive while taking part in this research study. However, scientists disagree on whether radiation doses at these levels are harmful. It is unclear whether already low doses of radiation could cause cancer. Even though no effects have been observed, some scientists believe that radiation can be harmful at any dose - even low doses such as those received during this research study.

Subjects will be asked to tell the research team if they have taken part in other research studies or received any medical care at any hospitals or any other place that used radiation. This is done to confirm that subjects will not receive excessive radiation. Examples of the types of radiation exposure considered include x-rays taken in radiology departments, cardiac catheterization, and fluoroscopy as well as nuclear medicine scans in which radioactive materials were injected into their body. However, the possibility exists for a rare reaction to any of the substances or procedures to which a subject is exposed.

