**To minimize the risks associated with radiation** We will ensure that the radiation exposure in each subject does not exceed Federal guidelines. Information about [11C]PBR28 dosimetry was obtained from published data as described above. The dose of radiation will be submitted for approval to the Yale University Radioactive Drug Research Committee (YU RDRC). All scans will be done in the presence of medical supervision and trained nursing staff in an institution specifically designed to support imaging studies. In the event of serious medical complications, the Yale University PET scan facilities have immediate access to or consultation with specialized medical units at the Yale-New Haven Hospital. Preparation of radiopharmaceuticals and execution of PET scans will be performed by radiochemists, physicians, and technologists of the Department of Diagnostic Radiology, Yale University School of Medicine. These professionals are qualified by training and experience in the safe use and handling of radionuclides. Subjects will be asked about their previous radiation exposure, and those who have had research exposure within the past year will be excluded if their cumulative annual exposure (including the present study) exceeds FDA limits.

No PET studies will be performed on pregnant or potentially pregnant women, as confirmed by pregnancy testing during evaluation and on each scan day before initiation of any scan procedures. If subjects are breastfeeding they will not be able to participate in this research study.

**To minimize risks associated with MRI**, each subject will fill out the Yale Magnetic Resonance Research Center MRI Safety Questionnaire before the study. Only subjects who fulfill the criteria by this questionnaire will be eligible for the study. In addition, subjects will remove all metal (watch, hair pins, jewelry) and change into scrubs immediately prior to the study and pass through the metal detector in the MRRC before entering the MRI room. If the subject has any metallic prostheses/implants they will be excluded from the study. If a subject becomes anxious during the scan they can request that the MRI scan be stopped.

**To minimize risks associated with pregnancy and breastfeeding** we will not enroll women who are pregnant or breast-feeding.

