##### **Dosimetry studies of [11C]PBR28 in humans**

Studies to date suggest that [11C]PBR28 binds to TSPO specifically and with high affinity and has the potential to serve as a ligand for *in vivo* imaging of microglial activation. PBR28 has been used in humans and have been shown to be safe and well tolerated after administration to healthy subjects (125,126). According to Brown et al. (127) “Intravenous injection of 11C-PBR28 (carrier PBR28,  $0.019 \pm 0.006 \mu\text{g/kg}$ ,  $n = 5$ ) produced no clinically observable effects. Blood pressure, pulse, and respiratory rate during the 2 h after injection as well as blood and urine tests on the next day had clinically insignificant changes. After injection of 11C-PBR28, brain, lungs, liver, heart, kidneys, spleen,

and urinary bladder were visually identified as source organs with moderate-to-high activity in most subjects. Lungs had the highest uptake, with a peak value of 35% injected activity ( $n = 6$ ) during the first frame acquisition (0–2 min). Peak values of the percentage injected activity in liver, kidneys, brain, spleen, heart, and gallbladder were 15%, 14%, 5%, 4.5%, 3.7%, and 1%, respectively, all occurring within 10 min. The residence times of organs were calculated from 2D planar images. The effective dose was 6.6  $\mu\text{Sv}/\text{MBq}$ , and the 3 organs with highest radiation-absorbed doses were kidneys (53  $\mu\text{Sv}/\text{MBq}$ ), spleen (26  $\mu\text{Sv}/\text{MBq}$ ), and lungs (22  $\mu\text{Sv}/\text{MBq}$ ).

Based on these numbers, the critical organ is the kidney (52.6 mSv/MBq, i.e., 194.7 mrem/mCi), and we estimate that the maximum allowable injection dose for [ $^{11}\text{C}$ ]PBR28 is 25.6 mCi per single injection. The proposed radioactivity dose is 20 mCi per single administration for this study, which is below the permissible single study radiation dosage of 25.6 mCi based on dosimetry calculations.

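### The radiation guideline is worded as effective dose in the risk section, but the 25.6 mCi injection ceiling follows only if 5 rem is a kidney-dose limit, and no cumulative kidney dose is shown

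*Combined protocol and SAP*

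**What the plan says.** Section V, Risks associated with radiation, plans "two injections of 20 mCi of [11C]PBR28, for a total of 40mCi of [11C]PBR28". It gives the resulting exposure as a dose that "from this study is equal to an effective dose equivalent of 1.628 rem", or 1.888 rem when a 15 mCi PiB scan is added. It declares both below a guideline that it states twice, each time as effective dose: "This guideline is an effective dose of 5 roentgen equivalents in man (rem) per scan and 15 rem/year".

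The same section covers a failed scan: "the subject may receive an additional radiotracer infusion(s), if deemed appropriate". It gives totals for one additional injection only, 2.44 rem without PiB and 2.70 rem with it.

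Section VI.A.2, Dosimetry studies of [11C]PBR28 in humans, quotes published coefficients, beginning "The effective dose was 6.6" microSv/MBq, with 53 microSv/MBq for the kidney. It names the kidney as the critical organ, prints its coefficient as 52.6 mSv/MBq or 194.7 mrem/mCi, and concludes: "we estimate that the maximum allowable injection dose for [ $^{11}\text{C}$ ]PBR28 is 25.6 mCi per single injection".

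Two places control annual exposure. Exclusion criterion 15 refers to the annual and total dose limits in 21 CFR 361.1. The paragraph on minimizing radiation risk says that "those who have had research exposure within the past year will be excluded if their cumulative annual exposure (including the present study) exceeds FDA limits". Neither names a dose metric.

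**The concern.** A limit on effective dose and a limit on dose to one organ are different constraints. For this tracer the kidney coefficient is several times the whole-body one, so the same injected activity can look remote from a limit on one metric and fairly close on the other. The risk section uses the first metric to state the margin; the dosimetry section appears to use the second to set the ceiling.

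The exposure statement, the annual-exposure exclusion and any decision to repeat a failed scan all draw on these figures. Repeats are a foreseen event: the sample-size text allows for failed scans, and the safety monitoring plan schedules a meeting on extra scans within one year. Staff reading only the risk section would not see how much margin remains on the metric that seems to have produced the ceiling.

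**Working it through.** **Inputs.** From Risks associated with radiation: 20 mCi per PBR28 injection, two planned; 1.628 rem for 40 mCi; 1.888 rem with PiB; 5 rem per scan and 15 rem/year. From Dosimetry studies: 6.6 microSv/MBq effective dose; kidney 53 microSv/MBq, also given as 52.6 and as 194.7 mrem/mCi; ceiling 25.6 mCi. Conversions: 1 mCi = 37 MBq; 1 rem = 10 mSv.

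**1. Reproduce the ceiling.**
- Kidney: 5,000 mrem / 194.7 mrem/mCi = 25.68 mCi, which truncates to the stated 25.6. With 53 microSv/MBq (196.1 mrem/mCi) it is 25.50 mCi.
- Effective dose implied by the risk section: 1,628/40 = 40.7 mrem/mCi, so 5,000/40.7 = 122.9 mCi.
- Effective dose from the quoted publication: 6.6 × 37/10 = 24.42 mrem/mCi, so 5,000/24.42 = 204.8 mCi.

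Only the kidney coefficient returns the stated ceiling.

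**2. Reproduce the repeat-injection totals.** One injection is 1.628/2 = 0.814 rem. Then 1.628 + 0.814 = 2.44 rem and 1.888 + 0.814 = 2.70 rem, as stated. These totals therefore cover one extra 20 mCi PBR28 injection and no more.

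**3. Cumulative dose on each metric.** The kidney column is n × 20 × 0.1947 rem, PBR28 only. PiB adds 1.888 − 1.628 = 0.260 rem to the effective figure.

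| PBR28 injections | Kidney, rem | Effective dose equivalent, rem | Same with PiB, rem |
|---|---|---|---|
| 1 | 3.89 | 0.81 | 1.07 |
| 2 (planned) | 7.79 | 1.63 | 1.89 |
| 3 (one repeat) | 11.68 | 2.44 | 2.70 |
| 4 (two repeats) | 15.58 | 3.26 | 3.52 |

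Per injection, 0.814 rem is 16% of 5 rem and 3.89 rem is 78%. For the planned two, 1.628 rem is 11% of 15 rem and 7.79 rem is 52%. On effective dose as stated, 15 rem is first passed at the 19th injection: 15/0.814 = 18.4, or (15 − 0.26)/0.814 = 18.1 with PiB. On kidney dose, 15 rem is reached at 15/3.894 = 3.85 injections.

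**4. PiB contribution to the kidney.** This is not given. With one PBR28 repeat, PiB would have to add more than 15 − 11.68 = 3.32 rem, that is 3.32/15 mCi = about 221 mrem/mCi, to reach 15 rem.

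**5. Whole-body figures.** 40 mCi = 1,480 MBq. At 6.6 microSv/MBq this is 9.77 mSv = 0.98 rem. The stated 1.628 rem corresponds to 11.0 microSv/MBq, a ratio of 1.67.

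**6. Unit.** 52.6 microSv/MBq × 37/10 = 194.6 mrem/mCi, which matches the printed 194.7. The printed mSv/MBq would be a thousand times larger.

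**The case against.** The strongest reply is that every scenario the protocol puts a number on stays within its figures whichever metric is used. One injection is 3.89 rem to the kidney, below 5. Two are 7.79 rem and three are 11.68 rem, both below 15 (PBR28 only). That stands.

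A reader might infer that the re-injection rule can breach the stated annual limit. The documents do not support this. The annual limit as worded is effective dose, and two repeats use 3.26 of 15 rem. The 15.58 rem result needs the annual figure to be an organ limit and two extra full-activity infusions. The dosimetry section mentions no annual limit, and even its 5 rem is back-calculated rather than stated.

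A reader might also infer that the annual-exposure check runs on the wrong metric. That is not shown either: exclusion criterion 15 and the risk-minimization paragraph point to federal limits without naming a metric, and the regulation's text is not in the documents.

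There are also safeguards. Repeats follow only an unsuccessful scan and a judgement that they are appropriate; prior exposure is asked about; the cumulative annual total includes this study; committee approval must precede enrolment; and a monitoring plan for extra scans is promised. These matter, but none states a number of repeats or a metric.

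Finally, the unit slip leaves the 194.7 mrem/mCi correct. The risk section also reports the larger whole-body figure, so that mismatch does not understate the exposure. Both replies are fair, and both items still need correcting.

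**Conclusion.** The inconsistency is real. The guideline is stated and applied as effective dose in one section, while the per-injection ceiling in another is obtainable only from a kidney dose. The planned exposure takes up about one ninth of the 15 rem figure on the first reading and about half on the second, and the protocol shows only the first. The repeat-infusion wording is broader than the single repeat it totals.

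This rests on three assumptions: that the ceiling was derived from 5 rem, which the arithmetic supports but the text does not say; that 1.628 rem is all tracer dose; and that repeats are given at 20 mCi. Kidney doses from PiB and transmission scanning are not given and are left out. The documents do not settle which metric governs. The primary outcome and its analysis are unaffected; the point concerns a safety threshold and the exposure figures given for subjects, and it should be put right.

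**What to change.** Reconcile Risks associated with radiation, the risk-minimization paragraph, exclusion criterion 15 and Dosimetry studies of [11C]PBR28, naming in each the dose metric to which the limit applies. Add a table of cumulative effective dose and critical-organ dose, with and without PiB, for every number of injections that the repeat-infusion wording permits, so that wording and totals agree. Reconcile 6.6 microSv/MBq with 1.628 rem, or label the two quantities separately and give the source of each. Correct the kidney coefficient's unit.

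Which metric governs, and how many repeats are allowed, is for the sponsor and the radiation committees to decide. Section II lists the radioactive drug and radiation safety approvals as pending, which makes that submission a natural place to do it. The cost is protocol wording, matching consent wording where these figures appear, and one dosimetry table. The small downside is that the stated margin may look less favourable.

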#### **Risks of MRI:**

Magnetic resonance (MR) imaging carries a risk for subjects who are claustrophobic or have pacemakers, metal pieces, aneurysm clips, large colored tattoos, or any other contraindications for MR. MR is a technique that uses magnetism and radio waves, not x-rays, to take pictures and measure chemicals of various parts of the body. The United States Food and Drug Administration (FDA) has set guidelines for magnet strength and exposure to radio waves, and we carefully observe those guidelines. Subjects will be watched closely throughout the MR study. Some people may feel uncomfortable or anxious. If this happens, the subject may ask to stop the study at any time and we will take them out of the MR scanner. On rare occasions, some people might feel dizzy, get an upset stomach, have a metallic taste or feel tingling sensations or muscle twitches.

These sensations usually go away quickly but we will ask subjects to tell the research staff if they have them. There are some risks with an MR study for certain people. If subjects have a pacemaker or some metal objects inside their body, they may not be in this study because the strong magnets in the MR scanner might harm them. Another risk is the possibility of metal objects being pulled into the magnet and hitting a subject. To reduce this risk, we require that all people involved with the study remove all metal from their clothing and all metal objects from their pockets. We also ask all people involved with the study to walk through a detector designed to detect metal objects. It is important to know that no metal can be brought into the magnet room at any time. Also, once subjects are in the magnet, the door to the room will be closed so that no one from outside accidentally goes near the magnet. We want subjects to read and answer very carefully the questions on the MR Safety Questionnaire related to their personal safety. We will be sure that subjects have read the MR Safety Questionnaire and tell us any information they think might be important. This MR study is for research purposes only and is not in any way a clinical examination. The scans performed in this study are not designed to find abnormalities. The PI's, the lab, the MR technologist, and the Magnetic Resonance Research Center are not qualified to interpret the MR scans and are not responsible for providing a diagnostic evaluation of the images. If a worrisome finding is seen on a subject's scan, a radiologist or another physician will be asked to review the relevant images. Based on his or her recommendation (if any), the PI or consulting physician will

09/29/12 Version 13

contact the subject, inform them of the finding, and recommend that they seek medical advice as a precautionary measure.

The decision for additional examination or treatment would lie solely with the subject and their physician. The investigators, the consulting physician, the Magnetic Resonance Research Center, and Yale University are not responsible for any examination or treatment that a subject receives based on these findings. The images collected in this study are not a clinical MR exam and for that reason, they will not be made available for diagnostic purposes.

